3.11. Visit Windows

Every effort should be made to ensure that all visits occur according to the protocol SOA, including any dropouts. All data will be tabulated per the evaluation visit as recorded on the CRF, even if the assessment is outside of the visit window. If the evaluation visit is missing in the database but there is data from an unscheduled or additional visit that is inside the visit window, the data from the unscheduled or additional visit will be used in data summaries. Specific visit windows will be defined in a separate specification document. Windows around analysis time points will be outlined below. All available data will be listed for each subject.

3.11.1. Analysis Window for Primary Analysis (i.e., ~52-Week Treatment) at the End of Period 2

The primary analysis will occur after the last enrolled patient has completed Period 2. i.e., \sim 52 weeks of treatment. An \pm 2 months window will be used for the primary endpoint. If a patient has a missing measurement at \sim 52 weeks of setmelanotide treatment but does have another non-missing measurement within 10-14 months (40-56 weeks) of active setmelanotide treatment, the measurement closest to 52 weeks will be used. If a patient has two non-missing visits within this window that are equidistant from 52 weeks, the earlier visit will be used.

Given the fact that patients are staggered entering into the study and randomized into active treatment or placebo in the initial 14-week period, some patients will already have more than 1 year (i.e., 52 weeks) of active treatment at the time of the data cut for NDA submission (Primary Analysis). It is also likely that some other patients will have less than 1 year of active treatment.

29

The examples below help to illustrate the approach outlined above:

- Example 1: A patient who was initially randomized to setmelanotide arm in Period 1, but may have already had 15 months setmelanotide treatment and available data at the time of the primary analysis. The patient's primary endpoint will be defined as the closest one to 52-weeks of active treatment within the 10-14 months window.
- Example 2: A patient who was initially randomized to placebo in Period 1 but may have already been in the study for 15 months, having received 3 months of placebo then 12 months of active setmelanotide. The patient's primary endpoint will be defined as the closest one to 52-weeks of active treatment within the 10-14 month window.
- Example 3: A patient who was initially randomized to placebo in Period 1 but may have been in the study for only 10 months, having received 3 months placebo then 7 months of active setmelanotide. The patient's primary endpoint will be defined as the patients ~12 months active treatment measurement as generated via multiple imputation method described above, since the patients active setmelanotide treatment duration is less than 10 months.
- Example 4: A patient who was initially randomized to placebo in Period 1 but may have been in the study for 14 months, having received 3 months placebo then 11 months of active setmelanotide. The patient's primary endpoint will be defined as the closest done to 52-weeks of active treatment within the 10-14 months window.

There are two planned visits in Period 3 (14-week open-label treatment): Visit 14 (~Week 60) and Visit 15 (EOS, ~Week 66). The analyses and summaries on data collected in this period will not be a main priority of the primary analysis for NDA submission or analyses in other regulatory agencies. However, an additional supportive analysis may be provided on these data after the approximately last patient in pivotal cohort completes the last visit at the end of period 3.

The additional supportive analysis and summary at end of period 3 will be based on relative visits/days (i.e., staggered alignment) from the first dose of the setmelanotide, below examples illustrate the staggered alignment for analysis,

- V2 (Week 1) of patients initially randomized in setmelanotide group (planned first dose visit of setmelanotide) will align with V6 (Week 15) of patients initially randomized in placebo group (i.e, planned first dose visit of setmelanotide).
- V13 (Week 53) of patients initially randomized in setmelanotide group (~52 week visit on setmelanotide) will align with V15 (Week 66) of patients initially randomized in placebo group (i.e, ~52 weeks visit on setmelanotide).
- Other visits will be aligned in a similar fashion.

3.11.2. Analysis Window for 14 Week Analysis

[figure not shown]
A +/-1-month (4-week) window will be used for the analysis and summary of the 14-week endpoints.

3.12. Interim Analyses and Timing of Planned Analyses

No formal interim analysis is currently planned for this study. However, various data cuts may occur in support of regulatory submissions such as a New Drug Application. The timing of these data cuts and the number of subjects included in each analysis will take into account

specific requests from regulatory agencies and applicable regulatory guidance. The rationale for each analysis will be documented.

The timing of the planned analyses:

4. STUDY ANALYSES

4.1. Subject Disposition

Subject disposition will be tabulated and include the number screened, the number randomized, the number treated in total, the number dosed with setmelanotide, the number dosed with placebo, the number in each subject population for analysis, and the number who withdrew prior to completing the study and reason(s) for withdrawal.

A by-subject data listing of study completion information including the reason for premature study withdrawal, if applicable, will be presented. Subject disposition will include patients in the Screening Analysis Set.

4.2. Demographics and Baseline Characteristics

Demographics and baseline characteristics will be summarized and presented by randomized treatment group and overall. Age at baseline as well as height, weight, and BMI at baseline and initiation of active treatment will be summarized using descriptive statistics (N, mean, 95% confidence interval of the mean, SD, median, minimum, and maximum). The number and percentage of subjects in each sex, ethnicity, race, and clinically- or genetically-defined genetic deficiency categories (BBS; all AS patients were required to be genetically identified to enter the trial) also will be presented. The percentage of cognitively impaired subjects will be provided. The Fitzpatrick Classifications Scale will also be summarized. No formal statistical comparisons will be performed. Subject demographics will include patients in the Safety Analysis Set. A separate demographics summary will be created for patients ≥12 years of age in the Full Analysis Set.

Medical history will be summarized in a table and presented in a by-patient listing.

4.3. Efficacy Analyses

In general, efficacy analyses will be conducted using the FAS population. Additional supportive analysis based on the DUS, CS, and/or PP Sets etc. may be provided as appropriate. Unless stated otherwise, all the analysis on hunger score data will be based on patients ≥12 years of age while only descriptive summary will be provided for patients <12 years of age (due to the different hunger score questionnaire tools). Descriptive statistics for endpoints analyzed at ~52 weeks will have their visits aligned by approximate relative day on setmelanotide (active treatment visit).

4.3.1. Primary Efficacy Analysis

The primary efficacy analysis on the primary efficacy endpoint will be conducted in patients ≥12 years of age (at informed consent) in the FAS population.

[figure not shown]
The primary efficacy endpoint is the proportion of patients (≥ 12 years of age) who achieve a $\geq 10\%$ reduction in body weight from baseline after ~ 52 weeks of treatment. The null hypothesis (H0) to be tested is that the proportion of patients treated for ~ 52 weeks who achieve $\geq 10\%$ reduction in body weight from baseline is less than or equal to a historical control rate of 10%. The alternative hypothesis (H1) is that the proportion is greater than a historical control rate of 10%:

H0: $p_t \le 10\%$ vs H1: $p_t > 10\%$

where p_t is the response rate after ~52 weeks of treatment.

Please note that there are two different uses of "10%" above, which is explained here for clarity:

- The use of "10%" in the endpoint definition is the **response criteria** for an individual patient. If a patient achieves a ≥10% reduction from baseline in body weight, the patient will be categorized as a responder in this analysis. Otherwise, the patient will be categorized as a non-responder.
- The use of "10%" as the historical control **rate** is the historical reference/control response rate to be statistically compared to the observed response rate in patients treated with setmelanotide. The observed response **rate** of setmelanotide will be calculated with the number of responders (using the above 10% endpoint definition) divided by the number of total patients.

The primary endpoint will have binomial proportions calculated for each of the 100 imputed datasets. The outcomes from the 100 imputed datasets will be combined using Rubin's Rule to provide an overall estimate against the null hypothesis with corresponding confidence intervals and p-value (Little and Rubin, 2002). The 1-sided 0.025 significant level was chosen based on the small sample size due to the rarity of the disease. The success criterion for the primary hypothesis requires the rejection of the null hypothesis at the 1-sided 0.025 significance level. The statistical criterion corresponds to the 2-sided 95% CI for setmelanotide of the response rate excluding 10% (i.e., lower bound of the CI >0.10).

This analysis may be repeated on the following analysis sets: DUS, PP at EOP2, SH, AG, as appropriate.

Body weight (kg) will be recorded as shown in the SOA (Table 1 and Table 2). Weight is repeated in triplicate and the mean weight calculated at study visit. Mean weight will be utilized for analysis purposes.

Descriptive statistics for the change and percent change from baseline in body weight (kg) may be presented in the FAS population by active treatment visit.

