Setmelanotide drug product (setmelanotide mPEG-DSPE formulation) is a sterile solution for injection. The product is manufactured at a concentration of 10.0 mg/mL.

Placebo is vehicle only and is identical in appearance to active treatment.

Setmelanotide and placebo will be administered as SC injection QD.

There will be extensive training of patients in drug administration including educational materials. Study-specific training materials will be provided to both the investigative staff and study participants and caregivers. Home nurses will be available, as needed, for additional training and to reinforce compliance. The Sponsor will provide extra placebo supplies for use during training.

Statistical Considerations

The primary statistical hypothesis is that the proportion of patients who are treated with setmelanotide for \sim 52 weeks who achieve \geq 10% reduction from baseline in body weight is greater than a historical control rate of 10% in the \geq 12 years old Full Analysis Set (\geq 12 yo FAS) (see definition in Section 8.2).

Data from the Clinical Registry Investigating Bardet-Biedl Syndrome (CRIBBS) were used to provide input for the sample size/power calculations. In particular, the natural history responder rate (percent of patients with weight loss ≥10% over a 1-year period) was assessed to determine the power estimates for the primary efficacy endpoint (see details in Section 8). The sample size is mainly driven by the primary hypothesis; although the rarity of the population is also taken into consideration.

Data from CRIBBS suggest that the proportion of subjects ≥ 12 years old who had $\geq 10\%$ spontaneous weight reduction from the previous 1-year period is approximately 6.4%. The power calculations assume a null historical control value of 10% who show at least a 10% weight loss, which is expected to be a conservative estimation. It is also expected that treatment with setmelanotide for ~ 52 weeks is associated with a true underlying probability of at least 66% who demonstrate at least 10% weight loss after ~ 52 weeks.

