A sample size of 7 patients provides ~95% power at 1-sided alpha of 0.05 and ~91% power at 1-sided alpha of 0.025, to yield a statistically significant difference compared to a historical control rate of 10%, based on a one-sample test, assuming a 66% response rate in patients who are treated with setmelanotide. The Sponsor has chosen 1-sided, alpha=0.05 as the scientific success criterion associated with the primary analysis.

Although these data suggest that powering the study for the primary endpoint will require a minimal number of patients (N<10), the size of the trial is also a function of the rarity of BBS and AS and a desire to better understand the effect of setmelanotide in these patient populations. Hence, approximately 30 patients (including 6 AS patients) are planned to be enrolled in the study. This number is suitable for a single pivotal trial to support the indications in BBS and AS and to provide robust information for both the between group analysis of the placebo-controlled, double-blinded period and the one-sample comparison to the historical control response rate after the planned 38 week open-label treatment period.

The primary analysis on the primary efficacy endpoint will be based on the \geq 12 yo FAS. By nature of the study design, a small percentage of patients who are randomized into the placebo arm may have less than \sim 52 weeks of setmelanotide treatment by the timing of the primary analysis (end of Period 2); hence, a linear model based extrapolation will be used to impute their measurements after \sim 52 weeks setmelanotide treatment for the primary analysis. In general, missing values unrelated to study treatment (eg, due to lost to follow-up or missed visit) will also be imputed with the linear model based extrapolation, but missing values due to treatment-related reasons (eg, lack of efficacy or AEs) will be imputed as treatment failures. A data snapshot will be taken for the primary analysis, and a supplemental supportive analysis will be performed on a locked database following study completion.

TABLE OF CONTENTS

CLINIC	AL STUDY PROTOCOL	1
APPROV	VAL SIGNATURE PAGE	2
INVEST	IGATOR STATEMENT	3
CLINIC	AL STUDY SYNOPSIS	4
TABLE	OF CONTENTS	10
List of Ta	ables	15
List of Fi	gures	15
LIST OF	ABBREVIATIONS	16
1.	INTRODUCTION	20
1.1.	Purpose of Study	20
1.2.	Overview of Bardet Biedl and Alström Syndromes	20
1.2.1.	Bardet Biedl Syndrome	20
1.2.2.	Alström Syndrome	21

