5.8. Prior and Concomitant Treatment

5.8.1. Permitted Medication

Female patients may use hormonal contraception as well as hormone replacement therapy.

Unless concomitant medications are likely to present a strong potential safety concern, the general goal of this protocol is to allow as many as possible patients with these ultra-rare conditions to participate in the study. Therefore, patients are allowed chronic concomitant medications (eg, as described below) while participating in the study:

- Growth hormone
- Contraceptives (see Section 6.2.1 for requirements for contraception)
- Hormone replacement therapy (eg, estrogen, progestins, androgens)
- Anti-hypertensives
- Statins and other lipid-lowering therapies
- Thyroxine or other thyroid supplements
- Other medications commonly used in obese patients including: endocrine therapies (eg, estrogens, bisphosphonates, hydrocortisone, vitamin and calcium supplements, diabetic therapies including insulin); and other medications (eg, carnitol, Coenzyme Q10, vitamins, anti-constipation medications, anti-allergic medications).
- Apart from low threshold drugs (eg, anticonvulsants, digoxin, warfarin sodium), other
 medications may be permitted if on a stable dose (for at least 1-2 months) upon
 consultation with the Sponsor.

There is little evidence that setmelanotide will result in drug interactions at present, but data are limited. Patients and caretakers should be carefully questioned about medication use to ensure that potential patients are carefully warned of possible side effects from drug interactions that could occur with the specific list of medications that an individual patient will be receiving.

Patients will be reminded at each visit that if it becomes necessary for a patient to take any other medication during the study, from Screening until the Final Study Visit, they must inform the study staff immediately, and the specific medication(s) and indication(s) must be discussed with the Investigator. All concomitant medications taken during the study must be recorded in the source documents and on the eCRF.

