5.8.2. Prohibited Medication and Substances

Medications, including those approved to treat obesity, that could impact the efficacy results of this study are prohibited (eg, orlistat, lorcaserin, phentermine-topiramate, naltrexone-bupropion, liraglutide).

Stimulant (and non-stimulant, if decreased appetite/weight loss is listed side effect) medication (eg, to treat attention deficit hyperactivity disorder [ADHD]) cannot be started during the study. Patients who have been on a stable dose and regimen for at least 2 months prior to study entry may continue to receive the same dose and regimen during the study.

Anorectic agents or drugs with anorexia as a non-rare side effect are prohibited for the duration of the study.

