5.8.3. Concomitant Procedures

Concomitant procedures conducted during the study, including those used to treat adverse events, are to be reported on the eCRF.

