2.2. Protocol Violations

At the discretion of the Sponsor, major protocol violations, as determined by a review of the data prior to unblinding of the study results and the conduct of statistical analyses, may result in the removal of a subject's data from the PP Set. The Sponsor or designee will be responsible for producing the final protocol violation file (formatted as a Microsoft Excel file), in collaboration with the data monitoring group (or designee) as applicable; this file will include a description each protocol violation and clearly identify whether or not this violation warrants exclusion from the PP Set. This file will be finalized prior to database lock. An analysis performed on the PP set may be provided only if the number of patients in the PP set is 20% less than that in FAS/PCS set.

All protocol violations will be presented in a data listing.

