3. GENERAL STATISTICAL METHODS

3.2. General Methods

All data listings that contain an evaluation date will contain a relative study day (Rel Day). Pre-treatment and on-treatment study days are numbered relative to the day of the first dose of study medication which is designated as Day 1. The preceding day is Day -1, the day before that is Day -2, etc.

All output will be sorted and labeled according to the International Conference on Harmonization recommendations and formatted to the appropriate page size(s).

Tabulations will be produced for appropriate demographic, baseline, efficacy, and safety parameters. For categorical variables, summary tabulations of the number and percentage of subjects within each category of the parameter will be presented. For continuous variables, the number of subjects (N), mean, 95% confidence interval of the mean, median, standard deviation (SD), minimum, and maximum values will be presented.

Formal statistical hypothesis testing will be performed on the primary efficacy endpoint with testing conducted at the 1-sided, 2.5% level of significance. Summary statistics will be presented, as well as confidence intervals (CIs), as described in the sections below. Trial success will be based on a 1-sided p-value <0.025.

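### A ≥10% weight loss reached after starting a prohibited drug, or after a weight-reducing procedure, is still credited to setmelanotide, because treatment failure applies only to missing weights

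*SAP*

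**What the plan says.** **Responder rule.** SAP 4.3.1 classifies each patient on weight: "If a patient achieves a ≥10% reduction from baseline in body weight, the patient will be categorized as a responder in this analysis". The population is the FAS aged ≥12. SAP 2.1 admits to the FAS anyone with one dose of setmelanotide and baseline data, with no exclusion for violations.

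**Failure rule.** SAP 3.10.2 replaces a ~52-week value by baseline only when it is missing for a reason other than the administrative data cut. SAP 4.3.4 restates this, and Protocol 8.4 also ties failure to missing values.

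**Other treatment.** Protocol 5.8.2 states: "Medications, including those approved to treat obesity, that could impact the efficacy results of this study are prohibited". Protocol 5.8.1 permits, among other chronic medication, "diabetic therapies including insulin". On procedures, Protocol 5.8.3 says only: "Concomitant procedures conducted during the study, including those used to treat adverse events, are to be reported on the eCRF". No readable section gives any of these a consequence in the analysis.

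**Comparison.** Placebo control ends at Week 14. The ~52-week test is against a constant (Protocol synopsis): "The power calculations assume a null historical control value of 10% who show at least a 10% weight loss". The synopsis derives it from a registry rate of about 6.4%, described as spontaneous weight reduction. SAP 3.2 sets the criterion: "Trial success will be based on a 1-sided p-value <0.025".

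**Possible check.** SAP 4.3.1 allows a repeat on the per-protocol set at the end of Period 2 (PP at EOP2), as appropriate. SAP 2.2 restricts per-protocol analyses: they "may be provided only if the number of patients in the PP set is 20% less than that in FAS/PCS set".

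**The concern.** The ban in Protocol 5.8.2 shows that the sponsor regards these drugs as able to distort the efficacy result. Exclusion 3 in Protocol 4.3 treats earlier gastric bypass with lasting weight loss in the same way at entry. Yet the SAP does not say what happens to the endpoint when such an event occurs on study.

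The situation need not produce a missing value. Patients who stop study drug are encouraged to attend all remaining visits (Protocol 4.5, SAP 3.9), so a weight taken after another therapy may well be observed, and it then enters the primary analysis unchanged. The handling is lopsided: a patient who leaves and is not weighed is a failure, whereas one who adds another weight-loss treatment can be a success.

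In a randomised comparison some of this would occur in both arms. Here there is no concurrent arm at ~52 weeks, and SAP 3.6 plans no covariate adjustment. What is at stake is the estimated response rate, the mean percent weight change and, if the drug's true effect is small, the error rate of the primary test.

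**Working it through.** **1. The plan's own power figure.** The Protocol synopsis gives n = 7, 66% against 10%, with power of about 95% (one-sided 0.05) and 91% (0.025). Under the arcsine approximation, power = Φ(h√n − z), with h = 2·asin√0.66 − 2·asin√0.10 = 1.253 and h√7 = 3.315:
- Φ(3.315 − 1.645) = 95.3%
- Φ(3.315 − 1.960) = 91.2%

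Both reproduce. The exact test gives 95.1% at 0.05 (≥3 responders) and 81.6% at 0.025 (≥4). The SAP's 0.025 is used below because SAP 1.1.1 says the SAP supersedes the protocol.

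**2. Inputs for the illustration.**
- Null 10% and one-sided 0.025: SAP 4.3.1.
- Number aged ≥12: not given. The pivotal cohort is 38 patients of all ages (SAP 1.1.1), so n = 20 to 38 is assumed.
- m, the number of affected patients: not given; m = 2 is assumed.
- q, an affected patient's chance of meeting the 10% criterion: assumed 1 or 0.5.

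**3. False success if setmelanotide does nothing.** Let r be the smallest count with P(Bin(n, 0.10) ≥ r) ≤ 0.025. Then

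P(false success) = Σₖ P(Bin(m, q) = k) · P(Bin(n − m, 0.10) ≥ r − k).

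| n | r | m = 0 | m = 2, q = 1 | m = 2, q = 0.5 |
|---|---|---|---|---|
| 20 | 6 | 1.1% | 9.8% | 4.0% |
| 28 | 7 | 1.8% | 11.2% | 5.1% |
| 32 | 8 | 1.2% | 7.3% | 3.3% |
| 38 | 9 | 1.1% | 6.3% | 2.9% |

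The exact test is discrete, so results jump with n. Over every n from 20 to 38 the three columns span 0.8–2.4%, 5.5–15.2% and 2.4–6.8%.

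**4. Two checks on the assumptions.**
- The SAP combines proportions by Rubin's rules and does not name an exact test. If success is instead a Wald lower 95% limit above 10%, r becomes 7, 8, 9 and 9 at the four sizes. The m = 2, q = 1 column becomes 2.8%, 4.0%, 2.6% and 6.3%.
- If the others respond at the registry's 6.4% rather than 10%, n = 32 with m = 2 and q = 1 gives 1.1%.

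**5. At the planned 66%.** Expected responders are 0.66 × 20 = 13.2, 0.66 × 32 = 21.1 and 0.66 × 38 = 25.1, against 6, 8 and 9 needed. To lose significance, about 8, 14 and 17 would have to be reclassified (for n = 32: 21 − 8 + 1 = 14).

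**6. Effect on the estimate.** One reclassified responder moves the rate by 100/n points: 5.0 at n = 20, 3.3 at n = 30, 2.6 at n = 38. Some affected patients would have responded anyway. Two certain responders at n = 30, compared with a 66% expectation, inflate the rate by 2 × (1 − 0.66)/30 = 2.3 points.

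**7. Power after the fix.** With a share c counted as failures, the response rate is 0.66(1 − c). At c = 20% this is 0.528, and power at one-sided 0.025 is 98.9% (n = 20) and 99.9% (n = 30).

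**8. The 20% condition.** 0.20 × 38 = 7.6, so at least 8 of the 38 pivotal patients must be excluded before the per-protocol analysis may appear. With 32 patients, six exclusions (6/32 = 18.75%) would not suffice.

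**The case against.** **A treatment-policy analysis is legitimate.** Using observed weight whatever else the patient takes is a recognised choice, and replacing it with a composite rule is partly preference. That stands in general. It is weaker here, because the reference is a fixed rate of spontaneous loss and not a concurrent arm exposed to the same co-treatment. The SAP also does not say that it has chosen this strategy.

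**Safeguards exist.** Investigators may withdraw non-adherent patients, and all violations are listed. These help only partly. Withdrawal is discretionary, and withdrawn patients may still be weighed. PP at EOP2 could drop a patient on a prohibited drug if the sponsor judges this a major violation, but a procedure is not listed as prohibited, and dropping a patient is not the same as counting a failure.

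**Stronger readings that the documents do not support.**
- *That any patient who takes a banned drug becomes a responder.* The patient must still show ≥10% loss from the active-treatment baseline.
- *That the type 2 diabetes rates in Protocol 1.2.2 indicate how many patients are affected.* They describe the syndromes, not treatment started after baseline; unchanged chronic therapy is already reflected in baseline weight.
- *That four or six affected patients show the real risk.* At n = 32 and q = 1 these give 30.5% and 74.9%, but about 8% and 16% at q = 0.5, and nothing in the documents supports such counts.
- *That Protocol 4.1 waives the medication exclusion on health grounds alone.* It also requires joint case-by-case review and the sponsor's written approval, and it concerns entry, not the on-study ban.
- *That Protocol 5.8.1 and 5.8.2 flatly contradict each other.* They can be read as a general permission with a specific prohibition. The boundary for diabetic therapies is nevertheless unclear, since liraglutide is named as prohibited.

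**Conclusion.** The gap is real and should be fixed before the database snapshot. A ≥10% loss measured after prohibited treatment or a weight-reducing procedure counts for setmelanotide, and no planned analysis reliably shows how much this matters.

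The size is conditional. Two affected patients certain to respond, with an ineffective drug, take the exact test from about 1–2% to 6–11% at the tabulated sizes. A 50% chance of responding gives 3–5%, and a Wald-type criterion or a 6.4% background rate gives less. The number of events, their chance of producing response and the number aged ≥12 are all assumptions. The documents do not say whether registry patients used weight-loss treatment, so the margin between 6.4% and 10% may absorb some of the effect.

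A reader might infer that trial success is in doubt. At the planned 66% it is not: roughly 8 to 17 responders would have to be reclassified. There the consequence is an overstated response rate and mean weight change. Some SAP and protocol sections are not readable, but those where such a rule would be expected (SAP 2.1, 3.9–3.11, 4.3.1, 4.3.4) contain none in their readable text.

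**What to change.** 1. Add to SAP 3.10.2 and 4.3.1: a patient who, before the ~52-week weight, starts a medication prohibited by Protocol 5.8.2 or has a weight-reducing procedure is a non-responder, with change set to 0 in the key secondary weight analysis.
2. Identify cases from the eCRF medication and procedure records before the database snapshot and without reference to the weight outcome. Blinding to the randomised arm is not enough, because everyone is on open-label drug from Week 15 and weights are visible.
3. Report the as-observed result as the sensitivity analysis.
4. Delete the 20% condition in SAP 2.2 so that PP at EOP2 is always reported for the primary endpoint.
5. List starts of permitted diabetic, thyroid or growth-hormone therapy descriptively. Do not count every dose change as failure: a dose reduced because the patient lost weight would turn a true responder into a failure.
6. Reconcile Protocol 5.8.1 with 5.8.2 for diabetic therapies, so that it is clear which starts fall under item 1.

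The cost is SAP wording, one review of data already collected and one extra analysis. The responder rate may fall slightly, and loss achieved before the event is not credited. Power at the planned effect stays near 99% or above even if 20% of patients are affected.
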